**Exploratory Objectives:**

To predict responses and examine the pharmacodynamics of treatment through the identification of unique biomarkers and transcriptomic changes of NL at week 0 and utilizing RNA sequencing on responsive and non-responsive tissue at week 4 To correlate these biomarkers with measures of global response: NL Lesion Score, PGA, and BSA.

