### **3.4 Primary Study Endpoints**

Change in NL score (0-12) of the index treatment lesions (weeks 0 and 12).

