## 7.2 Statistical Methods

### Descriptive Statistics

#### Sample Size Computation and Power Analysis:

The sample size for this pilot study is set at 12 subjects for logistical and financial reasons. This is similar in size to other exploratory studies and will provide adequate data for estimation purposes for planning future studies. With 12 subjects, the study is intended to be for estimation purposes only.

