### Bioinformatic Analysis:

RNA-seq analysis: We will use our recently developed LinNorm program

to process RNA-seq data and detect differentially expressed genes (DEGs) by comparing the RNA-seq profiles. We will first find DEG between responsive and non-responsive samples from the same individual by using paired or unpaired Wilcoxon rank-sum test (depending on how the samples are collected). We will then rank each gene in the DEGs based on the occurrence frequencies in all 12 subjects to find common DEGs for responsiveness (use permutation test to determine the p value). By comparing the normal tissue with the pathogenic tissue (responsive + non-responsive) using the above approach, we will detect a common DEGs for NL pathogenesis. Hierarchical clustering and Principal Component Analysis (PCA) will be applied to samples for their hierarchical relationship and clustering properties. Ideally normal, responsive and non-responsive tissues should form three distinct groups. The PCA analysis will provide us a set of gene signatures that can distinguish these three types of tissues. The common DEGs for responsiveness and pathogenesis, as well as gene signature from PCA will be used for our pathogenesis or survival

prediction. Additionally, we will perform de-convolutional analysis, to compare the immune profiles of responsive and non-responsive tissue and to correlate immune profiles. Predictive biomarkers will be correlated with lesional and global responses.

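### Response genes are selected by an undefined responsive/non-responsive split, although graded response is recorded and only a between-subject split of 12 is feasible

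*Combined protocol and SAP*

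**What the plan says.** The Bioinformatic Analysis part of Section 7.2 starts the search for response genes with a two-class comparison: "We will first find DEG between responsive and non-responsive samples from the same individual". The test is a "paired or unpaired Wilcoxon rank-sum test (depending on how the samples are collected"). Results are then pooled over subjects: "We will then rank each gene in the DEGs based on the occurrence frequencies in all 12 subjects", with a permutation p value. Graded response appears at the end of the same part: "Predictive biomarkers will be correlated with lesional and global responses". Section 2 states the aim behind it: "To correlate these biomarkers with measures of global response: NL Lesion Score, PGA, and BSA".

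The response scales are fine enough to use directly. The primary endpoint in Section 3.4 is "Change in NL score (0-12) of the index treatment lesions (weeks 0 and 12"). Section 14 builds that score from four items rated 0 to 3 and gives the PGA seven grades, 0 to 6. BSA is a percentage. Table-2 schedules all three at every visit from Day 0 to Week 16.

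No section says which scale, visit or threshold makes a sample responsive. Section 14 attaches complete, partial, stable and progressive labels to the PGA grades but does not tie them to the RNA-seq groups. The tissue visit also differs: Section 2 places responsive and non-responsive tissue at week 4, while the Study Summary and the exploratory outcome measures in Section 3.1 place it at week 12. Table-2 schedules biopsies only at Day 0 and Week 4.

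On size, Section 7.2 says: "The sample size for this pilot study is set at 12 subjects for logistical and financial reasons", and "With 12 subjects, the study is intended to be for estimation purposes only".

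**The concern.** Two things go wrong at the selection step.

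First, the contrast within a subject has no data. Section 3.1 provides three biopsies per subject: lesional and non-lesional skin at week 0, and one treated lesion at week 4. One treated sample can be labelled responsive or non-responsive, not both. What remains is a comparison between subjects, with group sizes fixed by the response rate and not by design.

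Second, that comparison uses one bit of response per subject where a graded value exists. Subjects who improved slightly more than an unstated threshold are treated like those who cleared. If nearly everyone responds, or nearly no one does, one group is too small for any gene to be declared, while graded scores can still differ. For example, if responsive meant a complete or partial response on the PGA, that class would cover grades 0 to 3.

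Section 7.1 presents biomarkers predictive of response as part of what the 12-subject design will deliver, so a selection step that may return nothing, or depend on a cut chosen after the data are seen, affects a stated purpose of the trial.

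**Working it through.** **Inputs from the documents.** n = 12 (Sections 3.2 and 7.2); one treated-lesion biopsy per subject and up to 36 samples (Section 3.1); a Wilcoxon test on two classes (Section 7.2).

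**Assumed, because the documents give none.** A two-sided 5% level per gene, the gene-response correlation, the response rate and the group split.

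**1. The plan's own figures.** There is no stated power to reproduce. The sample count agrees with the schedule: 12 × 3 = 36.

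**2. The within-subject contrast.** It needs at least one sample of each class per subject; the schedule gives one treated sample in total. Even one of each would not help: the smallest two-sided exact rank-sum p is 2/C(2,1) = 1.

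**3. The between-subject split.** The smallest attainable two-sided exact p with groups of k and 12 − k is 2/C(12,k):

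| Split | Smallest p |
|---|---|
| 6/6 | 2/924 = 0.0022 |
| 4/8 | 2/495 = 0.0040 |
| 3/9 | 2/220 = 0.0091 |
| 2/10 | 2/66 = 0.030 |
| 1/11 | 2/12 = 0.167 |

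A 1/11 split cannot reach 0.05, and 0/12 has no contrast. This needs no assumption about gene effects.

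**4. How likely that is.** With response rate π, the chance of at most one non-responder is π^12 + 12(1 − π)π^11. The chance of at most one responder is negligible at these rates.
- π = 0.7: 0.0138 + 0.0712 = 8.5%
- π = 0.8: 0.0687 + 0.2062 = 27%
- π = 0.9: 0.2824 + 0.3766 = 66%

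**5. Power if the relation is graded.** Simulation of 12 subjects, with expression and response bivariate normal. Spearman correlation on the graded response is compared with the exact Wilcoxon rank-sum test after splitting the response (40,000 runs per cell; loss in percentage points in brackets):

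| Correlation | Graded | 6/6 | 4/8 | 3/9 | 2/10 |
|---|---|---|---|---|---|
| 0.3 | 14% | 9% (5) | 10% (4) | 7% (7) | 5% (9) |
| 0.5 | 34% | 20% (14) | 21% (13) | 16% (18) | 10% (24) |
| 0.7 | 69% | 44% (25) | 43% (26) | 33% (36) | 20% (49) |
| 0.8 | 86% | 61% (25) | 60% (26) | 46% (40) | 30% (56) |

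Rounding the response to an integer score (SD 1, 2 or 3) gives losses of 12 to 57 points for correlations 0.5 to 0.8. The loss does not keep growing: at correlation 0.95 with a 6/6 split it is about 5 points, because both tests nearly always succeed.

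**6. A stricter level.** At 0.001 per gene no split has any power, since the smallest p is 0.0022. Spearman keeps about 3% at correlation 0.5 and 30% at 0.8.

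**7. Power if response is truly two-class.** Take correctly labelled classes, a 2-SD expression shift between them, a 4-point gap in score, and score variation within class (SD 1) unrelated to expression. The order reverses: Wilcoxon has about 83% at 6/6 against roughly 70% for Spearman, and about two thirds against one third at 3/9.

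**The case against.** The strongest reply is that the plan calls itself an estimation study with an exploratory biomarker aim, so power per gene is a secondary yardstick. That stands in part. Section 7.2 nevertheless picks genes by a test and a permutation p value, so the ability to detect matters at that step. In a full transcriptome screen neither method does well: assuming about 20,000 genes and a Bonferroni level, Spearman power is only about 0.05% to 2% for correlations 0.5 to 0.8. The figures above compare two methods; they do not promise findings.

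It is also fair that the power comparison prices a between-subject test, whereas the sentence describes a within-subject one. The plan's allowance for an unpaired test leaves room for this, and it is the only version that the biopsies support.

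Four stronger readings may tempt a reader, and the documents do not support them:
- That the plan explicitly dichotomises the NL score, PGA or BSA. It does not; it leaves the label undefined.
- That a gene missed by the split can never be related to graded response. The later correlation is not restricted in words to genes that passed the split. PCA signatures, immune profiles from deconvolution, and genes from the normal versus pathogenic comparison reach it by other routes.
- That a graded test always wins. It loses if response is truly two-class, and Supplemental 1 in Section 8.1 notes that the NL score is not validated, so differences within a class may be noise.
- That the split costs a fixed number of points. The loss depends on correlation, split and level, none of which the documents give.

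**Conclusion.** The point holds as a cheap improvement to an exploratory analysis. Three parts rest on the documents alone: the response classes have no stated scale, visit or cut-point; the contrast within a subject cannot be run with one treated biopsy; and a between-subject split of 12 cannot reach p<0.05 when one group has 0 or 1 subjects. How often that last case arises depends on the assumed response rate.

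The power loss is conditional on a monotone relation between expression and response and on an unadjusted two-sided 5% level. Under those conditions it is roughly 12 to 57 points per gene for assumed correlations of 0.5 to 0.8 and splits from 6/6 to 2/10, and about 4 to 9 points at correlation 0.3. The loss falls on response-gene selection, not on the whole biomarker programme. The two-class contrast should become secondary and defined; the evidence does not justify dropping it.

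**What to change.** In the Bioinformatic Analysis part of Section 7.2, make the main response-gene analysis a graded test across subjects. For each gene, relate week-0 lesional expression, and separately the week 0 to week 4 change in lesional expression, to the week 0 to week 12 change in NL score, by Spearman correlation or a linear model on log expression. Use permutation p values and control the false discovery rate, naming the set of tests that it covers. Repeat with PGA grade and change in BSA as supporting scales.

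Keep a two-class comparison between subjects as a supplement, with its scale, visit and cut-point stated before the data are seen. Remove the reference to both classes coming from the same individual, and reconcile the week-4 and week-12 statements about the tissue.

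The cost is plan wording and slightly different code; no new samples, visits or measurements are needed. There are two small downsides: the result reads less easily as a responder signature, and the main analysis loses some power if response is truly two-class, which the supplementary contrast would partly cover.

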Tissue will be collected for RNA sequencing at week 0 and 4. Blood collection will include the isolation at week 0, 2, 4, 8, 12. 5mL vials of blood which will be separated and the serum and cell

pellet will be stored for future analysis. Three skin biopsies will be taken during the study. At week 0, one 3mm tissue biopsy will be taken from lesional skin and one biopsy will be taken from non-lesional (adjacent but normal-appearing a minimum of 2 cm from the primary lesion but within the same anatomical subunit) skin. At week 4, a 3mm biopsy will be taken from a treated lesion (Ideally the same lesion as the initial biopsy, separated by a minimum of 1cm, or a similar lesion in the same anatomical subunit). The lesions will be chosen using full body photographs taken at week 0. From the biopsy specimen, a small piece of tissue (approximately 1 mm) will be cut and placed in a bottle labeled for RNAseq. The larger specimen will be placed in a bottle labeled for biobank storage. Both samples will be snap frozen and stored in the biobank. Once sample collection is completed for all samples, the tissues labeled for biobank storage will continue to be stored in the biobank and RNA sequencing will be performed on the tissue samples labeled for RNAseq (up to 36 tissue samples) and analysis will be performed. Paired analysis of treatment responsive and refractory lesions will be made as well as treated and untreated lesions.

**Nucleic Acid Extractions:** RNA will be extracted from a total of 50 um of fresh tissue using the Qiagen FFPE RNeasy Micro extraction Kit according to manufacturer's recommendation.

**RNA Transcriptome Sequencing:** RNA transcriptome sequencing will be carried out using commercially available techniques. Briefly, RNA libraries will be created using up to 100ng of RNA as starting material using the Illumina RNA TruSeq Library kit according to manufacturer's recommendation. Libraries will be QCed for quality and quantity using the Illumina TapeStation High Sensitivity tape. Paired-end sequencing will then be carried out on the Illumina HiSeq 4000 using 101bp insert fragments.

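### With three biopsies per subject, the within-subject Wilcoxon gene tests cannot flag any gene, and no false-discovery rule is stated for a test pooled across subjects

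*Combined protocol and SAP*

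**What the plan says.** Section 7.2, Bioinformatic Analysis, sets out three steps.

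- Step one is a gene-level test inside each subject: "We will first find DEG between responsive and non-responsive samples from the same individual by using paired or unpaired Wilcoxon rank-sum test". The choice between the paired and the unpaired form is left open: "by using paired or unpaired Wilcoxon rank-sum test (depending on how the samples are collected").
- Step two ranks genes by how often they occur across the 12 subjects, "to find common DEGs for responsiveness (use permutation test to determine the p value").
- Step three carries the method to disease against normal skin: "By comparing the normal tissue with the pathogenic tissue (responsive + non-responsive) using the above approach".

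The resulting common genes, together with a separate signature from principal component analysis, are to be used for prediction and correlated with response.

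Section 3.1 fixes the tissue supply: "Three skin biopsies will be taken during the study". Two are taken at week 0 (one lesional, one non-lesional) and one at week 4 from a treated lesion. Section 3.1 also promises a paired comparison of responsive and refractory lesions.

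On size, Section 7.2 says "The sample size for this pilot study is set at 12 subjects for logistical and financial reasons" and "With 12 subjects, the study is intended to be for estimation purposes only". Neither document section gives a gene-level significance threshold, the number of genes to be tested, or a false-discovery or family-wise rule.

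**The concern.** A rank test needs replication in the unit where it is applied. Step one applies it within a subject, who contributes one or two samples per tissue class. Step two counts per-subject verdicts, so if step one can give none, the procedure stops there.

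The natural repair is to pool the Wilcoxon test across subjects. Two further gaps then matter. Thousands of genes are tested with no stated error rate for the list. And an exact rank test on 12 subjects has a smallest attainable p-value that is coarse on the scale of a transcriptome-wide correction.

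At stake are the predictive biomarkers that Section 7.1 names as a product of the design. The responder contrast is the one that supplies them, and it is the one hit hardest.

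**Working it through.** **Inputs from the documents.** 12 subjects, not replaced on withdrawal (Section 4.4.1), so 12 is a maximum. Three biopsies each; 12 × 3 = 36, which agrees with the stated ceiling of 36 tissue samples. No power, alpha or gene count is given, so there is no statistical figure to reproduce.

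**Assumptions.** Two-sided exact tests; p<0.05 per gene if uncorrected; Benjamini-Hochberg at q = 5% if corrected; 20,000 genes, with a range of 10,000 to 25,000.

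**1. The test as written, within one subject.** The smallest two-sided rank-sum p is 2/C(n1+n2, n1).

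- 1 v 1: 2/C(2,1) = 2/2 = 1.0. A signed-rank test on one pair gives the same, 2/2^1 = 1.0.
- 1 normal v 2 lesional: 2/C(3,1) = 2/3 = 0.67.
- Responsive v non-responsive: one post-treatment biopsy gives one response class per subject, so there is nothing to compare.

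No gene can be flagged at any usual threshold. This result needs none of the assumptions on gene count or effect size.

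**2. Pooled across subjects, uncorrected.** Expected chance calls when no gene differs are 0.05 × 20,000 = 1,000 (500 to 1,250 over the range). The exact signed-rank test on 12 pairs attains 0.0425 rather than 0.05, which gives 0.0425 × 20,000 = 850.

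**3. Pooled across subjects, Benjamini-Hochberg at 5%.** Rejecting k genes requires the k-th smallest p to be at most k × q/m. No p can lie below the floor, so a non-empty list needs k ≥ floor × m/q.

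| Contrast | Floor | Minimum list, m = 20,000 | m = 10,000 to 25,000 |
|---|---|---|---|
| 12 pairs | 2/2^12 = 0.00049 | 196 | 98 to 245 |
| 6 v 6 | 2/C(12,6) = 2/924 = 0.0022 | 866 | 433 to 1,083 |
| 4 v 8 | 2/C(12,4) = 2/495 = 0.0040 | 1,617 | 809 to 2,021 |

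These are minimum list lengths. The genes need not all sit at the floor: for 12 pairs the next p-value is 4/4096 = 0.00098, and 0.00098 × 20,000/0.05 gives 391 genes there as an alternative. At q = 10% the minima for 20,000 genes fall to 98, 433 and 809.

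**4. How often the minimum is reached.** Simulation with 20,000 independent genes, normal data, shifts of 1 to 2 SD and 10 replicates:

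| Truly different | 12 pairs: corrected list size | 12 pairs: false share uncorrected | 6 v 6: corrected list size | 6 v 6: false share uncorrected |
|---|---|---|---|---|
| 1% | 0 | 81 to 83% | 0 | 83 to 93% |
| 5% | 0 to 1,025 | 45 to 48% | 0 | 48 to 72% |
| 10% | 426 to 2,070 | 28 to 31% | 0 | 31 to 55% |
| 20% | 1,999 to 4,144 | 14 to 17% | 0, except about 1,500 at 2 SD | 17 to 35% |

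For 4 v 8 the corrected list was empty in every scenario.

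**The case against.** The strongest defence has four parts.

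- **The wording may be loose.** A paired Wilcoxon could mean 12 pairs across subjects. But ranking genes by how many subjects show them needs a verdict per subject, so the per-subject reading is what the text describes.
- **The ranking and permutation step filters chance.** If each subject falsely called 5% of genes independently, about 45 of 20,000 null genes would recur in at least 4 of 12 subjects, and 0.2 in at least 6. That is a fair point about such a filter in general. Here per-subject calls cannot occur, and no recurrence cut-off or adjustment of the permutation p-value is stated.
- **An unpaired test is allowed.** Twelve normal v 24 lesional samples have a floor of 1.6e-9, so the floor does not bind. That test would ignore the pairing and treat two lesional samples from one subject as independent.
- **The work is exploratory and for estimation only.** This stands, and it lowers the severity. The primary endpoint does not depend on these lists.

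A reader might infer more than the documents support. It would be wrong to say that the lists are bound to be mostly chance or, after any correction, nearly empty. The false share depends on the unknown proportion of genes that differ; for 12 pairs it is below half from about 5% upward. Benjamini-Hochberg on 12 pairs gives usable lists when many genes differ. It would also be wrong to say that clustering and principal component analysis rest on these lists, since both are applied to samples. And error control is unstated rather than shown to be absent: the in-house program named for detecting genes may apply its own, but its output is not described.

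**Conclusion.** The point holds in two parts of different strength.

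The within-subject test fails as written. Its smallest p is 1.0 or 0.67, no gene can be flagged, and the within-subject responsive v non-responsive comparison has no data. This follows from the biopsy schedule alone.

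The pooled alternative is conditional, because the plan does not specify it. Uncorrected, about 1,000 of 20,000 null genes would be called. Corrected by Benjamini-Hochberg at 5%, responder v non-responder lists are practically empty at 6 v 6 and 4 v 8, while paired normal v lesional lists work only when many genes differ. These sizes rest on the assumed gene count, thresholds and responder split. The simulated ranges also rest on normal, independent genes; real genes are correlated, which makes list sizes more variable.

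The plan should be changed, but the exploratory purpose keeps this below the issues that bear on the primary endpoint.

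**What to change.** In Section 7.2, Bioinformatic Analysis, replace the per-subject tests and the frequency ranking with one moderated-variance model per gene across all subjects (limma-voom or equivalent).

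- Take normal v lesional and week 0 v week 4 as within-subject contrasts.
- Take responder v non-responder as a between-subject contrast with subject as a random or correlated block, or as a response-by-time interaction. Do not use fixed subject effects for the responder main effect. With 12 subject terms, 2 tissue-time terms and 1 responder term there are 15 columns but rank 14, because the responder term is a sum of subject terms.
- Declare genes at a Benjamini-Hochberg false discovery rate of 5%, report the adjusted values, and label the lists hypothesis-generating.

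The cost is wording and standard free software, with no extra tissue. The price is a distributional assumption in place of a rank test, and shorter lists than an uncorrected p<0.05 rule would give. The model removes the discrete floor; it does not supply the power that 12 subjects lack.

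### The permutation p value for common differentially expressed genes has no stated direction or permutation unit, and as written it cannot identify genes that change consistently across subjects

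*Combined protocol and SAP*

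**What the plan says.** Section 7.2, Bioinformatic Analysis, describes two steps.

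- **Call within a subject:** "We will first find DEG between responsive and non-responsive samples from the same individual by using paired or unpaired Wilcoxon rank-sum test", the choice of paired or unpaired depending on how samples are collected.
- **Combine across subjects:** "rank each gene in the DEGs based on the occurrence frequencies in all 12 subjects to find common DEGs for responsiveness (use permutation test", the permutation serving to give each gene its p value.

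The same method is then carried to disease against normal skin: "By comparing the normal tissue with the pathogenic tissue (responsive + non-responsive) using the above approach", leading to a second list of common genes.

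The section does not say whether up and down calls are counted separately, what is permuted, what cut-off defines a DEG, or how multiplicity is handled.

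Section 3.1 limits the tissue to three biopsies per subject. Two of them belong to the baseline visit: "At week 0, one 3mm tissue biopsy will be taken from lesional skin and one biopsy will be taken from non-lesional" skin. The third, at week 4, comes from a treated lesion. The total for sequencing is up to 36 samples.

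**The concern.** A gene common to the disease, or to response, should differ between tissue types in the same direction in most subjects. The quantity that carries the p value is instead a count of subjects in which the gene was called. If the call can never be made, the count carries no information. If the call can be made but the count ignores sign, the count measures how often a gene differs by a large amount, which is a different hypothesis.

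Section 7.2 feeds the common genes into later prediction, and section 7.1 cites biomarkers predictive of response as part of the case for the single-arm design. At stake is whether that gene list would be empty, or would be filled by variable genes instead of consistently changed ones.

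**Working it through.** **Inputs from the documents.** 12 subjects (section 3.2); per subject one non-lesional and one lesional biopsy at week 0 and one treated-lesion biopsy at week 4 (section 3.1); Wilcoxon call within the individual and permutation p value on the count (section 7.2). The plan's own sample figure reproduces: 12 × 3 = 36.

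**Step 1: the call as written.** The smallest exact two-sided rank-sum p with a and b samples is min(1, 2/C(a+b, a)).

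| Samples per subject | Arrangements | Smallest p |
|---|---|---|
| 1 vs 1 | 2 | 1.0 |
| 1 vs 2 (both lesional samples pooled) | 3 | 0.667 |
| 4 vs 4 (first balanced design below 0.05) | 70 | 0.029 |

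A signed-rank test on one pair also has a smallest p of 1.0. No gene is called in any subject at a conventional level, so all counts are 0 and the permutation p is 1 whatever is permuted.

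Steps 2 to 4 assume some other call, such as a fold-change cut-off, and a count that ignores direction. The documents state neither.

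**Step 2: 1 vs 1, labels swapped within subjects.** Swapping turns the difference d into −d and leaves |d| unchanged. All 2^12 = 4,096 swaps therefore give the same count, and p = 1 for every gene. A gene up in 12 of 12 and a gene up in 6 and down in 6 both score 12 with p = 1.

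**Step 3: 1 vs 2, labels rearranged within subjects.** There are 3 arrangements per subject, and the count is no longer fixed. Take normal = 0, both lesional samples = 1.5, cut-off 1.0. The true arrangement gives |1.5 − 0| = 1.5, which is called. Each of the other two gives |0.75 − 1.5| = 0.75, which is not called. So p = (1/3)^12 = 1.9 × 10⁻⁶. Reversing the sign in 6 subjects changes nothing: p is again 1.9 × 10⁻⁶.

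**Step 4: gene labels shuffled within subjects.** The null count is approximately Binomial(12, r), where r is the share of genes called. Illustrative assumptions: log-normal gene SDs with log-SD 0.3 to 0.7, the top 5% to 20% by absolute log-ratio called, no gene consistently changed.

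| r | Reject at count | Attainable level | No-change genes rejected |
|---|---|---|---|
| 5% | ≥ 3 | 2.0% | 6% to 9% |
| 10% | ≥ 4 | 2.6% | 8% to 13% |
| 20% | ≥ 6 | 1.9% | 8% to 16% |

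In the most variable tenth of genes the rejection rate was about 41% to 87%.

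**Step 5: a signed statistic.** Take the larger of the up and down counts under the same 4,096 swaps. A gene up in 12 of 12 gives p = 2/4,096 = 0.0005; 10 up and 2 down gives 0.039; 6 up and 6 down gives 1.0. A signed test separates the cases that the unsigned count cannot.

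**Step 6: the floor.** For Benjamini-Hochberg at 5% with an assumed 20,000 genes, k genes tied at the floor pass if 2/4,096 ≤ 0.05k/20,000, that is k ≥ 195.3. About 196 genes at the floor are needed before any passes.

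**The case against.** The strongest reply is that the plan is silent rather than wrong. It does not say that up and down calls are pooled, that the call is two-sided, or which labels are permuted, and a directional count would escape step 2. This stands. Steps 2 to 4 show what follows if an analyst fills the gaps in an obvious way; they do not describe a stated method.

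A reader might infer that p = 1 for every gene holds whatever call is used. The documents do not support that. Label swapping leaves the count unchanged only for a symmetric, unsigned call on one sample against one. With both lesional samples pooled, a consistent gene can reach a very small p, as step 3 shows. Under the Wilcoxon call as written, the empty list comes from the call and not from the permutation.

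A reader might also take the simulated rates as the plan's error rates. They are not: the call rule and gene SDs are assumed, and the plan's LinNorm processing is not modelled.

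The analysis is also exploratory, qualified in the exploratory outcome measures by whether the data allow it, in a trial meant for estimation only. Section 7.2 also has clustering, principal components, deconvolution and correlation with response. This limits the impact. It does not rescue the p value, which needs a definition before the data are seen.

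**Conclusion.** The point holds in a limited form. Followed as written, the procedure calls no gene in any subject, because the smallest within-subject p is 1.0 or 0.667; this rests only on the biopsy numbers, an exact two-sided test and a conventional significance level. Repairing the call alone is not enough if the count stays unsigned. It then gives p = 1 throughout for a single pair, cannot tell agreement from opposition for one against two, and under gene shuffling rejects no-change genes several times too often in an illustrative simulation. Those three results assume a substitute call and a direction-blind count.

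The stronger claim, that the plan prescribes a direction-blind test, goes beyond the text: direction and permutation unit are simply missing. The consequence is confined to the exploratory biomarker aim. The NL score primary endpoint is unaffected.

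**What to change.** In section 7.2, for the normal versus lesional contrast:

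- Replace the occurrence-frequency p value with one signed log-ratio per gene and subject, Day 0 lesional minus Day 0 non-lesional.
- Test its mean or t statistic across subjects by flipping the sign of whole subjects (4,096 flips with 12 subjects), keeping all genes of a subject together so that correlation between genes is preserved.
- Report occurrence counts only as description, split into up and down.
- State the multiplicity rule, and acknowledge the floor of 0.0005 and what it implies for the number of genes tested.

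The cost is a change of wording and a few lines of code on samples already planned. The drawback is the coarse p value: a gene list that survives correction needs many genes at or near the floor.

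This does not repair the responsiveness contrast. One treated biopsy per subject gives no responsive and non-responsive treated pair from the same individual, so that contrast needs its own restatement in section 7.2.
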